8.3 Safety Analysis

8.3.1 Adverse Events

All the adverse events (AEs) reported will be coded and classified according to the MedDRA (Medical Dictionary for Regulatory Activities) coding dictionary (Version 17.0 or higher). Each adverse event is to be evaluated for date of start and end, seriousness, severity, causal relationship with the study drugs, action taken and outcome.

All AEs will be listed by patient and treatment.

The total number and percentage of patients with at least one AEs, discontinued study drug due to AEs, AE severity and AEs related to investigational product, serious AEs and death will be summarized by treatment groups and overall.

A summary table of the number and percent of patients with AEs by system organ class, preferred term, and treatment group will be presented. Each patient will be counted only once within each preferred term.

A frequency summary table of the number of AEs by system organ class, preferred term, severity, and treatment group will be presented. Severity will be classified as "Mild", "Moderate", or "Severe".

Similarly, a frequency summary table of the number of AEs by system organ class, preferred term, and relationship to a study drug, and treatment group will be presented. Relationship to a study drug will be classified as "Related" or "Not Related".

Should sufficient data exist, adverse event frequencies will be compared between treatments using the Chi-square testing (Fisher's exact test if appropriate).

Estradiol Vaginal Cream USP, 0.01%

Protocol/Study Number 71436001

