9.5.2 Visit 2 (Day 1): Randomization

1. **Medical History:** Patient's medical history including concomitant medication use since last visit will be reviewed.
2. **Inclusion/Exclusion:** Confirm the patient meets all inclusion/exclusion criteria.

CONFIDENTIAL PROTOCOL

A Randomized, Double-Blind, Placebo-Controlled, Parallel Design, Multiple-Site Study to Evaluate the Therapeutic Equivalence of Estradiol Vaginal Cream USP, 0.01% (Teva Pharmaceuticals, USA) to Estrace® Estradiol Vaginal Cream, USP, 0.01% (Warner Chilcott) in the Treatment of Atrophic Vaginitis

3. **Vital Signs:** Blood pressure, pulse, temperature and respiration rate will be recorded.
4. **Symptom Rating:** Patients will be asked to complete a rating scale to record severity of signs and symptoms for atrophic vaginitis. Refer to Appendix A.
5. Dispense study medication, applicator, instructions and patient diary to patients eligible for randomization.
6. Schedule Visit 3.

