9.7 Adverse Events

The patients will be monitored throughout the study for any adverse experiences. AEs will be collected through both solicited and unsolicited means and subsequently coded in tabular form using the MedDRA Version 17.0 or higher adverse event dictionary. The patients will be encouraged to report signs, symptoms, and any changes in health to the clinic staff. Severity of each AE will be determined by the clinic staff based on observation and questioning of the patient. The Investigator will judge the relationship of the event to the study treatments.

Definitions

An adverse event is any untoward medical occurrence in a clinical investigational patient administered a pharmaceutical product, regardless of whether it has a causal relationship with this treatment. In this study, any adverse event occurring after the patient has signed the informed consent form should be recorded and reported as an adverse event.

An adverse event can, therefore, be any unfavorable and unintended physical sign, symptom, or laboratory parameter that develops or worsens in severity during the course of the study, or significant worsening of the disease under study or of any concurrent disease, whether or not considered related to the study drug. A new condition or the worsening of a pre-existing condition will be considered an adverse event. Stable chronic conditions (such as arthritis) that are present before study entry and do not worsen during the study will not be considered adverse events.

Abnormal results of diagnostic procedures, including laboratory findings, are considered to be AEs if the abnormality:

- results in study withdrawal
- is associated with a serious adverse event (SAE)
- is associated with clinical signs or symptoms
- is considered by the physician to be of clinical significance

CONFIDENTIAL PROTOCOL

A Randomized, Double-Blind, Placebo-Controlled, Parallel Design, Multiple-Site Study to Evaluate the Therapeutic Equivalence of Estradiol Vaginal Cream USP, 0.01% (Teva Pharmaceuticals, USA) to Estrace® Estradiol Vaginal Cream, USP, 0.01% (Warner Chilcott) in the Treatment of Atrophic Vaginitis

This includes events not seen at baseline, or worsened if present at baseline.

Recording and Reporting Adverse Events

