For adverse event recording, the study period is defined for each patient as that time period from signature of the informed consent form through the follow-up period. For this study, the follow-up period is defined as 30 days after the last study visit.

All adverse events that occur during the defined study period must be recorded on the source documentation and transcribed onto the CRF, regardless of the severity of the event or judged relationship to the study drug. For serious adverse events, the Serious Adverse Event Form must also be completed and the serious adverse event must be reported immediately (see Section 9.8.2.). The investigator does not need to actively monitor patients for adverse events once the study has ended.

At each contact with the patient, the investigator or designee must query the patient for adverse events by asking an open-ended question. All reported or observed signs and symptoms will be recorded individually, except when considered manifestations of a medical condition or disease state. A precise diagnosis will be recorded whenever possible. When such a diagnosis is made, all related signs, symptoms, and any test findings will be recorded collectively as a single diagnosis on the CRF and, if it is a serious adverse event, on the Serious Adverse Event Form.

The clinical course of each adverse event will be monitored at suitable intervals until resolved or stabilized or returned to baseline, or until the patient is referred to the care of a health care professional, or until a determination of a cause unrelated to the study drug or study procedure is made.

The onset and end dates, duration (in case of adverse event duration of less than 24 hours), action taken regarding study drug, treatment administered, and outcome for each adverse event must be recorded on the source documentation and transcribed onto the CRF.

The relationship of each adverse event to study drug treatment and study procedures, and the severity and seriousness of each adverse event, as judged by the investigator, must be recorded as described below.

Severity of an Adverse Event

The severity of each adverse event must be recorded as 1 of the choices on the following scale:

Mild: No limitation of usual activities

Moderate: Some limitation of usual activities

Severe: Inability to carry out usual activities

CONFIDENTIAL PROTOCOL

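### AE summaries and tests are not restricted to treatment-emergent events and name no analysis end, and shell T16.1.9.9 leaves per-patient severity and relatedness unclear

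*SAP*

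**What the plan says.** **Recording.** Protocol 9.7 states that "any adverse event occurring after the patient has signed the informed consent form should be recorded and reported as an adverse event", and for this purpose "the follow-up period is defined as 30 days after the last study visit". The same section adds that "The investigator does not need to actively monitor patients for adverse events once the study has ended". Serious-event reporting under Protocol 9.8.2 has a different start, the first dose.

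**Analysis.** SAP 8.3.1 codes, lists and summarises every reported AE. If enough data exist, "adverse event frequencies will be compared between treatments using the Chi-square testing", with Fisher's exact test where appropriate. Neither the text nor any AE shell defines treatment-emergent events, applies a first-dose cut or names an end date. The Safety population requires one dose, which limits patients but not event dates.

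**Severity and relatedness.** A sentence in 8.3.1 opens "The total number and percentage of patients with at least one AEs" and goes on to list severity, relatedness, serious events and death, by treatment group. Later, for severity, "A frequency summary table of the number of AEs by system organ class, preferred term, severity, and treatment group will be presented", and a matching table is planned for relationship to study drug. Relationship has two categories, both in 8.3.1 and in the Protocol 9.7 causality table.

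**The concern.** An event that starts before the first dose cannot be caused by study drug. Counted as an AE of the arm, it adds the same expected background to every arm and pulls a comparison of patients with AEs toward no difference. The plan sets no rule on this, so whatever sites happen to record before dosing enters the summaries and tests.

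For severity and relatedness, a reader comparing arms needs the proportion of patients affected. A share of the arm's own events answers another question and can rank the arms differently. The footnote matters because it defines which events count as related.

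At stake is the safety comparison in Objective 3.

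**Working it through.** **1. The recording window.** Consent comes at screening (Day -14 to Day -1), Visit 3 falls on Day 8 or 9, and recording runs 30 days beyond it.
- Longest: 14 + 9 + 30 = 53 days; 7 dosing days are 7/53 = 13%.
- Shortest: 1 + 8 + 30 = 39 days; 7/39 = 18%.

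Most of the recordable window is off treatment, and up to 14 days of it precede the first dose.

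**2. Are pre-dose events likely to be captured?** The passages point both ways.
- Against: the study schematic in each document marks AEs only at Visit 3. The Visit 2 list (Protocol 9.5.2) has no AE item, and its dispensing step is "Dispense study medication, applicator, instructions and patient diary to patients eligible for randomization", so no diary exists earlier. Changes before Visit 2 can go into medical history (9.6.3). Visit 3 asks about AEs since the last visit (9.5.3).
- For: Protocol 9.7 says "At each contact with the patient, the investigator or designee must query the patient for adverse events by asking an open-ended question".

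Capture is probably small, but the documents do not settle it.

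**3. Illustrated dilution.** The documents give no AE figure to reproduce. Arm sizes come from the randomized total: 625/0.95 = 658, against 660 stated; at 2:2:1, 660 × 2/5 = 264 per active arm and 660/5 = 132 placebo.

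Assumed, not documented: weekly background risk b; an 8-point drug-caused risk during treatment; d screening days; a captured fraction c of pre-dose AEs.
- Pre-dose risk: pre = c × [1 − (1 − b)^(d/7)]
- On treatment: active 1 − (1 − b)(0.92); placebo b
- Follow-up: 0, or 1 − (1 − b)^(30/7) if fully captured
- Windows combine as 1 minus the product of (1 − risk)

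Example with b = 5%, d = 7, c = 1 and no follow-up events: on treatment, active is 1 − 0.95 × 0.92 = 12.6% and placebo 5.0%. Adding the pre-dose week gives 1 − 0.95 × 0.874 = 17.0% and 1 − 0.95 × 0.95 = 9.75%. The difference is multiplied by 1 − pre, so it shrinks but keeps its sign.

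Exact two-sided Fisher power at 0.05, 264 vs 132, no AEs captured after Visit 3:

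| b per week | From first dose | Half capture, d = 3/7/14 | Full capture, d = 3/7/14 |
|---|---|---|---|
| 0.5% | 98% | 98/97/95% | 97/95/91% |
| 1% | 95% | 93/91/88% | 92/88/80% |
| 5% | 67% | 62/55/47% | 56/47/36% |
| 10% | 46% | 41/35/29% | 36/28/21% |

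The lower two backgrounds suit a single-term row, the upper two the any-AE row. With no pre-dose capture the loss is zero in every row.

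If the 30 follow-up days were also fully captured, power before adding any pre-dose events would be 83%, 66%, 23% and 12% in the same row order. Full pre-dose capture would then cost a further 2 to 10 points (single term) or 1 to 4 points (any AE). The choice of end date can thus matter more than the first-dose cut. Full follow-up capture is an upper bound, since active monitoring is not required once the study has ended.

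**4. Denominators in the shells.**
- T16.1.9.10.1 and .10.2: patients, for any AE and by term, with a Fisher p-value. Not by severity or relatedness.
- T16.1.9.9: severity and relatedness rows sit under *AEs reported*, with no stated unit or base and no rule for a patient with several AEs. The only N row is *Patients Randomized*, in a table titled Safety Population.
- T16.1.9.11, .12 and .14: percentages of the arm's total events.

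A constructed example shows that event shares can mislead. Active: 40 of 264 patients have AEs, 26 of them with one related event each, plus 34 unrelated events (60 in all). Placebo: 18 of 132 patients have AEs, 4 with three related events each and 14 with one unrelated event each (26 in all).
- Related share of events: 26/60 = 43% vs 12/26 = 46%.
- Patients with a related AE: 26/264 = 9.8% vs 4/132 = 3.0% (Fisher p = 0.015).
- Patients with any AE: 40/264 = 15.2% vs 18/132 = 13.6% (p = 0.76).

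**5. The footnote.** T16.1.9.9 defines *Related* as Probable, Possible or Unlikely. The protocol scale has only Reasonable Possibility (related) and No Reasonable Possibility (not related), and SAP 8.3.1 has only Related and Not Related. The footnote's three categories are on neither scale.

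**The case against.** - **A reader might infer that there is no end of window at all.** The documents do not support that. The SAP is to be read with the protocol, which ends recording 30 days after the last visit, and an analysis of all reported AEs inherits that end. What is missing is a treatment-emergent subset and an analysis end chosen on purpose.
- **The visit procedures largely close the pre-dose gap.** This has real weight. The general instruction to query at each contact keeps the question open, but near-zero capture is plausible.
- **The larger power losses stack assumptions.** They need full pre-dose capture, assumed rates, no follow-up events and, at the extreme, 14 screening days for everyone. The test is also conditional and secondary. This stands, so the figures show a mechanism and do not forecast a loss.
- **A reader might infer that per-patient severity and relatedness were left out.** The text of 8.3.1 can be read as promising them, so the defect is an unclear shell. The percent-of-events bases appear only in the shells, which SAP section 9 describes as general layout open to change. Listing L16.2.7 allows patient-level derivation.
- **The share example is constructed.** It needs repeat events in four placebo patients. With one event per patient, the share can reverse only if the arm's total-AE ratio exceeds its related-AE ratio, and T16.1.9.10.1 would then already show the excess. Even with repeats, its term rows would show it if the related events share one term.
- **The footnote is confined to one shell.** On the protocol scale no event should be rated Unlikely, so actual miscounting is not established. The contradiction remains.

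**Conclusion.** The point holds as a clarification worth making. As written, SAP 8.3.1 credits any recorded pre-dose AE of a dosed patient to her arm and chooses no analysis end within the protocol's recording period. The effect is dilution toward no difference; in expectation it does not reverse the comparison. Its size is unknown and may be near zero, and every power figure above rests on assumed rates and capture.

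Two further defects need no assumed rate. T16.1.9.9 does not state its unit or base and labels its N row with a different population from its title. Its footnote contradicts the causality scale in both documents.

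Overall and per-term AE incidence per patient is already planned and tested in T16.1.9.10.1, so a broader claim that the safety comparison is unusable is not supported. Efficacy conclusions are unaffected.

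**What to change.** In SAP 8.3.1, base the AE summaries and the chi-square or Fisher tests on treatment-emergent AEs: onset or worsening on or after first dose, to a stated end such as the protocol's 30 days after the last visit. List pre-dose AEs separately. Choosing the 30-day end removes only the pre-dose dilution and keeps follow-up events in, so it should be a stated choice.

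In T16.1.9.9, show patients by maximum severity and patients with any related AE over the Safety population N per arm. Relabel the N row as Safety population and change the footnote to *Related = Reasonable Possibility*. Keep T16.1.9.11, .12 and .14 as event-count supplements.

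The cost is minor: SAP wording, one shell and some programming. AE start dates (SAP 8.3.1) and first-dose date (listing L16.2.5.2) are already collected, so no new data are needed.

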8.3.2 Vital Signs

The patient's vital signs will be recorded (pulse, blood pressure, temperature and respiration rate) at Visits 1, 2, and 3 or end of study.

Descriptive summaries (n, mean, standard deviation, minimum, median and maximum) will be provided by treatment and visit. The summary table will be based on safety population randomized.

All data will be listed by treatment and patient.

8.4 Statistical Analysis Issues

As this is a multiple-site study, treatment-by-site interaction analysis will be examined using the Cochran-Mantel-Haenszel Test for the primary efficacy variable, the proportion of patients in the PPP that are considered to be a "responder" at Visit 3. A site(s) with a low enrollment rate(s) may be pooled with its geographically closest site. The pooling will be done for low enrolling sites that account for less than 4-7% of the total number of patients in the PP population (equivalence test) and mITT population (superiority tests) at the site with the highest enrolling rate.

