8. STATISTICAL ANALYSIS METHODS

If not otherwise specified, statistical significance is defined as p<0.05 and is two-tailed. Data will be summarized with respect to demographic and baseline characteristics, efficacy variables and safety variables.

For categorical variables, the number and percent of each category within a parameter will be calculated for non-missing data. For continuous variables, statistics will include n, mean, standard deviation, median, minimum and maximum values.

All statistical analyses will be conducted using SAS®, Version 9.4 or higher. Datasets will be prepared using headings from Clinical Data Interchange Consortium (CDISC) Study Data Tabulation Model (SDTM) implementation for human clinical trials and ADaM (Analysis Dataset Model).

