8.1.2 Demographic and Other Baseline Characteristics

Baseline comparability of all treatment groups will be evaluated separately in the PP, mITT and Safety populations. The following baseline demographics (determined from their initial study visit) will be evaluated:

- Age (years)
- Gender (male/female)
- Ethnicity (Hispanic/non Hispanic)
- Race (White, Black/African American, Native Hawaiian or Other Pacific Islander, Asian, American Indian or Alaska Native, Other)
- natural or surgical menopause
- duration of postmenopausal status
- baseline signs and symptoms
- baseline % of the three major vaginal wall cell types (basal/parabasal cells, intermediate cells and superficial cells)
- vaginal pH

Summary tables by treatment group will be presented. Continuous variables will be summarized using descriptive statistics (n, mean, standard deviation, median, minimum, maximum).

Categorical variables will be summarized using frequencies and percentage. Baseline treatment comparisons will be presented using Cochran-Mantel-Haenszel test for the categorical variables, and Analysis of Variance for the continuous variables.

All data will be listed by treatment and patient.

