	$xx.x \pm xx.xx$	$xx.x \pm xx.xx$	$xx.x \pm xx.xx$	$xx.x \pm xx.xx$	X.XXXX
	XX.X	XX.X	XX.X	XX.X	
	xx.x - xx.x	xx.x - xx.x	xx.x - xx.x	xx.x - xx.x	

Test: Estradiol Vaginal Cream, USP, 0.01% (Teva Pharmaceuticals, USA)

Reference: Estrace® Cream (estradiol vaginal cream, USP, 0.01%; Warner Chilcott)

Placebo: Placebo cream (Teva Pharmaceuticals, USA)

 $Path: L: \Studies_Sas_Codes \Clinical\ Trial \71436001 \PDF \xxx$

Created on: ddmmmyy hh:mm

Page 4 of 5

T16.1.9.4 Summary of Baseline Demographic Data (Safety Population)

		Test (N = xxx)	Reference $(N = xxx)$	$ Placebo \\ (N = xxx) $	P-value
% of intermediate cells	n	XXX	XXX	XXX	X.XXXX
	$Mean \pm SD$	$xx.x \pm xx.xx$	$xx.x \pm xx.xx$	$xx.x \pm xx.xx$	
	Median	XX.X	xx.x	XX.X	
	Range	xx.x - xx.x	xx.x - xx.x	xx.x - xx.x	
% of superficial cells	n	XXX	XXX	XXX	x.xxxx
	$Mean \pm SD$	$xx.x \pm xx.xx$	$xx.x \pm xx.xx$	$xx.x \pm xx.xx$	
	Median	xx.x	xx.x	xx.x	
	Range	xx.x - xx.x	xx.x - xx.x	xx.x - xx.x	
Vaginal pH	n	XXX	XXX	XXX	x.xxxx
	$Mean \pm SD$	$xx.x \pm xx.xx$	$xx.x \pm xx.xx$	$xx.x \pm xx.xx$	
	Median	xx.x	XX.X	XX.X	
	Range	xx.x - xx.x	xx.x - xx.x	xx.x - xx.x	

Test: Estradiol Vaginal Cream, USP, 0.01% (Teva Pharmaceuticals, USA)

Reference: Estrace® Cream (estradiol vaginal cream, USP, 0.01%; Warner Chilcott)

Placebo: Placebo cream (Teva Pharmaceuticals, USA)

 $Path: L: \Studies_Sas_Codes \Clinical\ Trial \F1436001 \PDF \end{tens}$

Created on: ddmmmyy hh:mm

Page 5 of 5

Similar tables will be created for T16.1.9.5 and T16.1.9.6

T16.1.9.5 Summary of Baseline Demographic Data (modified Intent-to-Treat Population)

T16.1.9.6 Summary of Baseline Demographic Data (Per-Protocol Population)

T16.1.9.7 Summary of Analysis Results of Primary Efficacy Endpoint (Proportion of Responders Between Treatment Groups)

Equivalence: Per-Protocol Population

				Difference Between Treatments		
Treatment	Number of	Number of	Proportion of			
Group	Patients (N)	Responders (n)	Responders (%)	Difference	90% CI Evaluation	
Test	XXX	XXX	XX.X%			
Reference	XXX	XXX	XX.X ⁰ / ₀	XX.X%	xx.x - xx.x	

Superiority: modified Intent-to-Treat Population

				Treatment	vs. Placebo
Treatment	Number of	Number of	Proportion of		
Group	Patients (N)	Responders (n)	Responders (%)	Difference	P-value
Placebo	xxx	xxx	xx.x%		
Test	xxx	xxx	xx.x%	xx.x%	x.xxxx
Placebo	xxx	xxx	xx.x%		
Reference	XXX	xxx	xx.x%	xx.x%	x.xxxx

Test: Estradiol Vaginal Cream, USP, 0.01% (Teva Pharmaceuticals, USA)

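### SAP 8.4 uses the Cochran-Mantel-Haenszel test to look for treatment-by-site interaction, which that test does not measure; the site-pooling cut-off is also left open

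*SAP*

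**What the plan says.** SAP 8.4 states that "treatment-by-site interaction analysis will be examined using the Cochran-Mantel-Haenszel Test for the primary efficacy variable", meaning responder status at Visit 3 in the per-protocol (PP) population. It gives no significance level of its own, so the general default in SAP section 8 applies: "If not otherwise specified, statistical significance is defined as p<0.05 and is two-tailed". It does not name the pair of arms to be compared or say what follows from a positive result. Neither the SAP nor the protocol names a homogeneity test or a treatment-by-site model term. The only other use of CMH is in SAP 8.1.2, as a comparison of treatment groups: "Baseline treatment comparisons will be presented using Cochran-Mantel-Haenszel test for the categorical variables".

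On small sites, 8.4 says "A site(s) with a low enrollment rate(s) may be pooled with its geographically closest site". The next sentence reads "The pooling will be done for low enrolling sites that account for less than 4-7% of the total number of patients", refers to both the PP and the modified intent-to-treat (mITT) populations, and ends "at the site with the highest enrolling rate".

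**The concern.** A test of average association and a test of heterogeneity answer different questions. Effects in opposite directions at different sites tend to cancel in CMH, so real disagreement can pass unnoticed. A difference that is the same at every site accumulates in CMH and can be reported as an interaction that does not exist. If opposite effects cancel only partly, CMH may reject, but because of the net average effect.

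At stake is the statement about consistency across sites in the study report. A trial that meets the equivalence criterion could be described as having a site interaction when it has none, or as consistent when its sites disagree in direction.

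The pooling rule adds a smaller problem. The threshold is a range, the percentage can be taken of the whole population or of the largest site, the first sentence permits pooling while the second requires it, and no time is set for the choice.

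**Working it through.** **Inputs from the documents.** PP size is 224 per active arm, and mITT size is 250 per active arm and 625 in total, with up to 660 randomized (protocol 10.2, SAP 5). The level is 0.05 two-sided (SAP 8). Equivalence requires the 90% interval to lie within ±0.20 (SAP 8.2.1). The sample-size chain reproduces: 224/0.90 = 248.9, stated as 250; 625/0.95 = 657.9, stated as 660.

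**Assumptions.** The documents give no number of sites, no site sizes and no visible responder rates. I took 6, 8, 10, 14 or 20 equal sites (37 down to 11 patients per arm per site) and mid responder rates of 30, 40, 50 and 60%, the mid rate being the average of the two arms.

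**Statistics.** At site i, let x be Test responders, m all responders, n_T and n_R the arm sizes and N = n_T + n_R.

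- CMH = [Σ(x − E)]² / ΣV on 1 df, with E = n_T·m/N and V = n_T·n_R·m(N − m)/[N²(N − 1)].
- Breslow-Day-Tarone = Σ(x − A)²/v − [Σ(x − A)]²/Σv on (sites − 1) df. A is the count fitted under the common Mantel-Haenszel odds ratio, and v = 1/[1/A + 1/(n_T − A) + 1/(m − A) + 1/(n_R − m + A)].

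CMH sums the signed site deviations before squaring. The homogeneity test squares them first.

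**Two-site example.** Site 1 has Test 80/112 and Reference 32/112; site 2 is the reverse. At each site m = 112, N = 224 and E = 112 × 112/224 = 56, so the deviations are +24 and −24.

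- CMH: (24 − 24)² = 0, so p = 1.0.
- Breslow-Day-Tarone: the common odds ratio is 1, so A = 56 and v = 1/(4/56) = 14. The statistic is 2 × 24²/14 = 82.3 on 1 df, p about 1e-19. The Tarone term is zero.

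**Simulation.** Share of trials with p < 0.05, from 8,000 trials per scenario, shown as the range over the site layouts and rates above:

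| True Test − Reference difference | CMH | Breslow-Day-Tarone |
|---|---|---|
| None at any site | 4.5-5.6% | 4.7-6.9% |
| +20 points at half the sites, −20 at half | 4-5% | 75-97% |
| +10 points at half, −10 at half | 4-5% | 21-39% |
| ±20 points, about a 70/30 split of sites | 29-65% | 66-95% |
| Uniform 5 points, no interaction | 18-21% | 5-7% |
| Uniform 10 points, no interaction | 55-64% | 5-7% |

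**Link to the primary analysis.** The SAP's interval is (P_T − P_R) ± [1.645·se + (1/n_T + 1/n_R)/2]. With 8 to 20 sites and 20,000 trials per scenario:

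- Cancelling ±20 points: 98.6-99.7% of trials pass equivalence.
- Uniform 5 points: 92-96% pass, and CMH is significant in 11-18% of those.
- Uniform 10 points: 63-73% pass, and CMH is significant in 30-50% of those.

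**Pooling.** The cut-off at 4% and at 7%, in patients:

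- Whole mITT: 0.04 × 625 = 25 to 0.07 × 625 = 43.75.
- PP Test plus Reference: 2 × 224 = 448, giving 17.9 to 31.4.
- Largest site, assumed to have 40 to 100 patients: 0.04 × 40 = 1.6 to 0.07 × 100 = 7.

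**The case against.** The strongest reply is that nothing confirmatory depends on this check. The equivalence interval and the placebo Z-tests in SAP 8.2.1 have no site term, equivalence rests on the primary endpoint alone, and 8.4 attaches no decision to the result. That stands, and it limits the point to a supportive analysis.

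The flag rates also treat a CMH p-value below 0.05 as a reported interaction, whereas 8.4 says only that interaction will be examined. The rates are conditional on that reading. It is the natural one, given the SAP's default level and the absence of any other criterion.

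The scenarios are illustrative. A 20-point reversal equals the whole equivalence margin and is a stress case, and at ±10 points the homogeneity test itself detects only 21-39%. This is a fair limit on the proposed test, and a reason to show site-level estimates beside it. It does not rescue CMH, which stays at 4-5% there.

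SAP 9 says the table shells are a framework to be modified, so the lack of a site line in T16.1.9.7 is weak evidence. It remains true that no planned summary shows response by site; T16.1.9.3.2 gives patient counts only. The use of CMH in 8.1.2 is likewise only corroboration: the argument rests on what the test computes.

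On pooling, the largest site is arguably the more literal base, and on that reading the range spans only a few patients. Protocol 9.4.3 sends the randomization to the statistician only after database lock, which limits treatment-informed pooling before then but not afterwards. The pooling wording is a minor drafting gap and would not merit a comment alone.

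**Conclusion.** The concern holds. Followed as written, SAP 8.4 can give a wrong answer about consistency across sites. In the scenarios examined it almost never detects balanced reversals of effect (4-5%, no more than the nominal level), and it flags a uniform 10-point difference as interaction in more than half of trials. The direction of the error follows from the form of the statistic and needs no assumption. The percentages rest on equal sites, 6 to 20 of them, mid rates of 30-60% and a 0.05 level. The equivalence and superiority conclusions, their error rates and the sample size are not affected. This should be corrected, but it does not threaten the primary result.

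**What to change.** In SAP 8.4:

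1. Replace CMH with the Breslow-Day test with Tarone adjustment (an exact homogeneity test if site tables are sparse) or a treatment-by-site term in a logistic model, for Test against Reference in the PP population. If the check is also meant for superiority, repeat it for each active arm against Placebo in the mITT population.
2. State the significance level. With 8 to 20 sites, moving from 0.05 to 0.10 raises detection at ±10 points from 21-34% to 32-47%, with 10-13% false flags. This is a choice for the sponsor.
3. Present the Test − Reference difference with its 90% interval for each (pooled) site. The homogeneity test works on odds ratios while the margin is on the difference scale, and its power against moderate disagreement is low.
4. State that the result is supportive and does not alter the equivalence or superiority decision. Keep CMH, if wanted, only as a labelled site-stratified analysis of the average effect.
5. Give one pooling threshold and one base (for example, sites with under 4% of the PP population), make pooling mandatory in both sentences, and fix the pooled sites before the randomization is released.

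The cost is SAP wording and one site-level table. No new data are needed and the primary analyses do not change.
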